In animals, WS extracts have also been shown to be safe in toxicity studies. Acute and sub-acute toxicity of a hydroalcoholic root extract of WS was investigated in female Wistar rats.⁴⁴ No behavioral signs of toxicity or gross pathological changes were observed with acute doses up to 2000 mg/kg. Similarly, no signs of subacute toxicity were observed in rats given 500, 1000 or 2000 mg/kg of the extract daily for 28 days. In a separate study, a hydroalcoholic root extract of WS was used to assess prenatal developmental toxicity in rats at doses of 500, 1000 and 2000 mg/kg daily for 28 days.⁴⁵ No signs of toxicity, gross pathology changes, or mortality were observed in the pregnant rats or fetuses. Further studies are required to examine the safety of WS extracts prepared using other extraction methods and plant parts.

In humans, the widespread use of WS as a traditional medicine and dietary supplement, as well as current scientific literature, support its general safety. In a review of clinical trials that used root preparations of WS for a wide variety of conditions, the authors noted that reasonable safety outcomes were seen with no serious adverse events or changes in vital signs or hematological and biochemical parameters.⁴⁶ Mild to moderate transient adverse events including somnolence, giddiness, vertigo, drowsiness, and gastrointestinal effects (e.g., nausea, epigastric pain, loose stools, constipation, decreased appetite) were reported in some studies, while other studies involving adults and children did not report any adverse events.⁴⁶ Similarly, an earlier review reported that WS has been used in all age groups and in both sexes, even during pregnancy, without any reported side effects.¹⁰ One study formally measured the tolerability of a WS root extract using the Patient's Global Assessment of Tolerability to Therapy and found it to have a high tolerability score.⁴⁷ Rare, serious adverse events have been reported, however. Isolated cases of mild to severe liver toxicity have occurred, with three deaths in patients who had underlying liver disease.⁴⁸⁻⁵⁰ A case report has also been published detailing a kidney transplant rejection due to WS.⁵¹ Liver and renal abnormalities will be assessed at the beginning and end of each four-week study period.

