Study Title: Safety, tolerability, and pharmacokinetics of an oral *Withania somnifera* product in older adults

Principal Investigator: [name], ND, MS

IRB#: STUDY00026055

Version Date: 10.10.2024

F.2. Study Population

F.2.1. Number of participants

Twelve non-demented older volunteers (6 female, 6 male) 65 years of age or older will be screened and enrolled in the study. We estimate that we will need to screen approximately twenty potential participants to meet the twelve volunteers needed to complete the study. We expect two dropouts, for a total of 10 participants completing the study.

F.2.2. Inclusion and exclusion criteria

Inclusion criteria:

1. Age 65 and older, male and female
2. Body Mass Index (BMI) greater than 17 and less than 35 at screening
3. Sufficient vision and hearing to complete all tests
4. Willingness to discontinue all botanical supplementation for one week prior to and throughout study
5. No known sensitivity to *Withania somnifera* or any of its derivatives
6. Normal or clinically not significant 12-lead electrocardiogram (ECG) recording
7. Hepatic (ALT, AST, bilirubin), renal (creatinine, estimated GFR), and TSH parameters within normal range
8. Hemoglobin ≥ 13.0 g/dL or hematocrit $\geq 39\%$ (males) OR hemoglobin ≥ 12.5 g/dL or hematocrit $\geq 38\%$ (females), per FDA recommendations on blood donation
9. General health status that will not interfere with the ability to complete the study
10. Willingness to attend all study visits
11. Willingness to avoid caffeine and xanthine-containing foods or beverages (e.g., coffee, tea, chocolate, caffeine-containing sodas, colas, etc.), as well as grapefruit juice and poppy-containing foods for 48 hours prior to baseline visits
12. Willingness to adhere to special diet (no dairy, grapefruit products, poppy-containing foods, high-fat meals, caffeine, or xanthine-containing foods or beverages) during baseline visits and until after 24-hour visit
13. Mini-Mental State Exam (MMSE) score ≥ 27

Exclusion criteria:

1. Current smoking, alcohol, or substance abuse according to DSM-V criteria
2. Participants who are currently pregnant, actively trying to conceive a child, or planning to within three months of study completion
3. Severe aversion to venipuncture
4. Donation of blood within 90 days of screening
5. Participation in drug research study within 90 days of screening

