Tolerability and safety: Participants' weight, height, body mass index, age, blood pressure, temperature, respiration rate, and pulse rate will be recorded at each study visit to monitor for adverse events and asymptomatic illnesses that may impact study results. Vitals will be collected at baseline, 7 hours post-Shoden administration, and at the end of each baseline visit. At the beginning of each baseline visit, participants will complete an electrocardiogram (ECG) and the Geriatric Depression Scale-15. Four teaspoons of blood (20 ml) will be collected for safety labs (CBC, CMP, urinalysis, TSH, serum total testosterone). ECG will be repeated 7 hours post-intervention to assess for cardiac changes. One teaspoon (5 ml) will be collected for a repeat CMP at 10 hours post-intervention to evaluate kidney and liver function. Participants will be interviewed and administered a standardized multi-system adverse events questionnaire at the beginning and end of each baseline visit. This visit is expected to take 13 hours a total of 175 mL of blood will be collected.

If the baseline CBC shows hemoglobin or hematocrit levels below what is recommended by the FDA for blood donation, the visit will be halted immediately. Participants will be asked to stay for 2.5 hours after the study agent has been administered to assess for acute side effects. Two and a half hours was chosen because common withanolides have reached their C_{MAX} by this time based on a previous PK study using Shoden®.⁸⁰ The end-of-visit adverse events questionnaire will be administered by phone and missed safety evaluations (7-hour ECG and vitals, 10-hour CMP, 12-hour vitals) will be collected at the 24-hour visit. After the 24-hour visit, the participant will be withdrawn from the study.

If study staff have difficulties collecting blood samples for any reason, the decision may be made to halt the visit. Participants will be asked to stay for 2.5 hours after the study agent has been administered to assess for acute side effects. If the visit ends before the 7-hour mark, the end-of-visit adverse events questionnaire will be administered by phone and missed safety evaluations (7-hour ECG and vitals, 10-hour CMP, 12-hour vitals) will be collected at the 24-hour visit. Participants will be allowed to remain on the study if difficulties with blood sample collection were the only reason for halting the study visit early.

I.4.2 24- and 48-Hour Visits

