★ Adverse events questionnaire administered at beginning and end of baseline visits

♦ If PK Visit 1 is ≥14 days since the screening visit

▼ REDCap surveys will be delivered to participants' email during the week prior to each study visit.

^ An ECG and CMP will be collected at the 24hr visit if the baseline visit was halted prior to the 7hr ECG and CMP being collected.

J. STUDY DURATION

Recruitment and data collection is expected to begin upon approval from the IRB and continue for nine months. We estimate a total of six months for final data analysis. Total estimated study duration is 21 months (Table 2).

Table 2. Study timeline.

Activity	Month																							
	1-3			4-6			7-9			10-12			13-15			16-18			19-21			22-24		
Characterization studies																								
Product quality control																								
LC/MS Method Optimization																								
Recruitment/enrollment																								
Data collection																								
Plasma/urine LC/MS analysis																								
PK data analysis/summary																								
Reports, manuscripts																								

K. DATA AND SPECIMENS

The principal investigator will oversee the management of the participants, intervention, and analysis, which will be carried out by the clinical investigators, research statistician, and research assistant. Data entry, quality control and preparation, and participant management will be ongoing throughout the study.

K.1. Data collection methods

The case report forms for this study include a telephone screening script, a medical history form, a cognitive screening questionnaire (Mini Mental State Examination), a mood screening questionnaire (Geriatric-Depression Scale-15), a stress questionnaire (Perceived Stress Scale (PSS)), a sleep questionnaire (Pittsburgh Sleep Quality Index (PSQI)), an adverse events questionnaire, and a 2-week follow-up phone script. Other data collection methods include administering an electrocardiogram, urine collection, and blood collection. The PSS and PSQI will be delivered to participants' emails via REDCap.

K.2. Handling of data and specimens

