To reduce pregnancy risk, participants will be instructed at the Exit Phone Call to contact the study team if they believe they are pregnant or have fathered a child post-study. A records review will be conducted by a member of the study team one month after each participant has completed the study to check for reports and outcome of pregnancy.

N.1. Attribution to intervention

Items identified on the Adverse Event Monitoring Form will be compared to baseline levels to determine if the symptom was preexisting. If the symptom was pre-existing at the same or a previously greater severity, the symptom will not be considered attributable to the study intervention. If the symptom was pre-existing at lesser severity (or was not previously present), the symptom may be considered attributable to the study intervention. If the intervention is considered attributable, the co-investigators and the PI will determine if an alternative clinical explanation exists for the adverse event. If an alternative explanation does not exist, the adverse event *will* be considered attributable to the study intervention. If an alternative

Study Title: Safety, tolerability, and pharmacokinetics of an oral *Withania somnifera* product in older adults

Principal Investigator: [name], ND, MS

IRB#: STUDY00026055

Version Date: 10.10.2024

explanation does exist, the adverse event will *not* be considered attributable to the study intervention.

N.2. Plan for review and reporting

The study team will submit continuing review questionnaires to the OHSU IRB per institutional policy. The PI will review protocol deviations, reports, and AEs in real time to determine if they must be reported as Reportable New information (RNI). Events that are RNI will be reported to the OHSU IRB per RNI policy. All other events will be summarized and reported at continuing review.

O. RISKS AND BENEFITS

O.1. Risks to subjects

Potential harm to participants will be minimized by excluding participants with the conditions detailed in section F.2.2. The risks to the subjects participating in this proposed research project are mainly those associated with venous access, potential toxicity of the test material, and time commitment.

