Venipuncture: The potential risks to participants are minimal and reversible. Likely risks include pain and bruising from the intravenous catheter or venipuncture needle insertion. Occasional risks include feeling lightheaded or faint during or immediately after a blood sample is collected. Unlikely risks include swelling, infection, transient hematomas, transient thrombophlebitis, a fractured catheter embolus, or an allergic reaction to the adhesives or sterilization materials used at the venous access point. To minimize risk, catheter insertions and blood draws will be conducted in a seated position and using aseptic technique by trained personnel.

Study Diet: The study diet requires that participants avoid any caffeine for 48 hours prior to each baseline visit. If participants regularly drink caffeinated beverages like coffee, they may experience symptoms of caffeine withdrawal, including headache, fatigue, decreased energy/activeness, decreased alertness, drowsiness, decreased contentedness, depressed mood, difficulty concentrating, irritability, and feeling foggy/not clearheaded.⁸⁵

Shoden® extract: Shoden® is a 70% ethanolic extract of *Withania somnifera* root and leaves, standardized to 35% withanolide glycosides and produced in a good manufacturing practice (GMP)-certified facility. We will also conduct independent analyses of impurities (pesticides, heavy metals, microbes) through Oregon's Wild Harvest (Redmond, OR) and confirm dose levels through analysis at Oregon State University (Corvallis, OR).

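### No adverse-event baseline is both unexposed to the product and free of the caffeine restriction, so mild drowsiness or fatigue can be misclassified

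*Combined protocol and SAP*

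**What the plan says.** Section I.4.1 sets the timing: "Participants will be interviewed and administered a standardized multi-system adverse events questionnaire at the beginning and end of each baseline visit". The Table 1 footnote agrees: "Adverse events questionnaire administered at beginning and end of baseline visits". Screening has no such questionnaire, either in the I.3 list of assessments or in the Table 1 row.

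O.1 (Study Diet) states: "The study diet requires that participants avoid any caffeine for 48 hours prior to each baseline visit". It warns regular users that "they may experience symptoms of caffeine withdrawal, including headache, fatigue, decreased energy/activeness, decreased alertness, drowsiness" and other complaints may follow. Inclusion criterion 12 in F.2.2 continues the diet, caffeine included, "during baseline visits and until after 24-hour visit".

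I.4.2 adds a questionnaire at the 48-hour visit and makes it the baseline for the four weeks of daily use. The same section allows that visit to be eliminated for later participants if no withanolides are found at 48 hours in the first two. A Table 1 footnote then moves the dispensing of the 35-day supply to the 24-hour visit. It says nothing about the questionnaire.

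N.1 compares symptoms with baseline and rules: "If the symptom was pre-existing at the same or a previously greater severity, the symptom will not be considered attributable to the study intervention". A symptom that was milder at baseline, or absent, may be attributed, subject to a search for another explanation. N.1 does not say which baseline applies to which phase, and it does not mention symptoms caused by the study diet.

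**The concern.** Both sequences receive active product and there is no placebo, so comparison with baseline is the first filter on attribution. L.2 reports possible relation to study drug for each treatment-emergent event, which makes attribution an Aim 2 output.

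The symptoms that O.1 expects from caffeine withdrawal overlap with a reported class of Withania effects. C.2.3, reviewing trials of root preparations, lists "Mild to moderate transient adverse events including somnolence, giddiness, vertigo, drowsiness, and gastrointestinal effects" in some studies. If a participant is already drowsy before dosing because of the diet, drowsiness of the same grade reported later is set aside as pre-existing. A reference taken before the restriction would show whether that drowsiness was usual for the participant. The plan has no such reference, and it cannot be recovered once data collection has started.

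**Working it through.** The documents give no figure for this point. The only power statement (L.4) concerns C_max and is not involved. The check sets the questionnaire schedule against the caffeine window, with hours counted from the single dose.

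| Contact | Exposed in this period? | Under caffeine restriction? |
|---|---|---|
| Screening | No | No, but no questionnaire is given |
| Start of baseline visit | No | Yes, 48 h |
| End of baseline visit | Yes, about 12 h after dose | Yes, about 48 + 12 = 60 h |
| 24-hour visit (no questionnaire scheduled) | Yes | Yes, about 48 + 24 = 72 h; then lifted |
| 48-hour visit | Yes, single dose | No, lifted about 48 − 24 = 24 h earlier |
| Two-week call, four-week visit | Yes, daily use | No |

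**Result of the comparison.** No row with a questionnaire reads No in both columns.

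**Single-dose phase.** The start- and end-of-visit questionnaires are both taken under restriction. Error can go two ways:
- Withdrawal drowsiness before dosing masks product drowsiness of no greater severity.
- Withdrawal symptoms that appear or worsen between about 48 and 60 hours of abstinence may be attributed to the product, unless the investigators name withdrawal as the alternative explanation.

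**Four-week phase, 48-hour visit kept.** The named baseline is free of the restriction but follows a dose. The caffeine mechanism does not act through it.

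**Four-week phase, 48-hour visit eliminated.** This could affect up to 12 − 2 = 10 of the 12 participants. If the questionnaire disappears with the visit, the start-of-visit one is the only pre-dose reference, and unrestricted two- and four-week reports are compared with a restricted baseline. If it moves to 24 hours, it is both post-dose and still under restriction.

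**Illustration of size, on assumed rates.** Let p be the true rate of product drowsiness, and w the independent share of participants whose withdrawal drowsiness at the reference was of equal or greater severity. Then:

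attributed rate = p(1 − w)

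P(at least one attributed event among 12) = 1 − [1 − p(1 − w)]^12

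For p = 10% and w = 25%: 0.10 × 0.75 = 0.075, and 1 − 0.925^12 = 60.8%.

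| w | p = 10%: attributed rate | chance of ≥1 | p = 20%: attributed rate | chance of ≥1 |
|---|---|---|---|---|
| 0 | 10% | 71.8% | 20% | 93.1% |
| 10% | 9% | 67.8% | 18% | 90.8% |
| 25% | 7.5% | 60.8% | 15% | 85.8% |
| 50% | 5% | 46.0% | 10% | 71.8% |

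With the 10 completers that F.2.1 expects and p = 10%, the chances are 65.1%, 61.1%, 54.1% and 40.1%. The formula covers only masking, not the opposite error.

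**The case against.** The case against is substantial, and most of it stands.

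- **Like with like.** Measuring background symptoms under the same diet, just before dosing, is a sound control for diet-caused symptoms. This holds for the single-dose phase, so the start-of-visit questionnaire should stay as its reference.
- **The four-week phase has its own baseline.** This holds only while the 48-hour visit is kept, and that baseline is still post-dose.
- **Worsening is still caught.** N.1 allows attribution above baseline severity, Section N also asks an open question about feeling different since starting, and L.2 tabulates treatment-emergent events with their relation rather than attributed events alone. The signal is reduced, not removed.
- **A screening reference alone would achieve little.** In the single-dose phase, a symptom first seen at the start of the visit would still be explained by the diet under N.1. By period 2, screening would be at least six weeks old (four weeks of use plus at least two of washout). This is why a second pre-restriction questionnaire is needed.
- **Other data exist.** The screening examination, medical history, GDS-15, and the PSQI and PSS in the week before each PK visit help in part. None is the questionnaire that N.1 compares. The washout call occurs only if washout exceeds 21 days, and Table 1 lists no questionnaire for it.

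A reader might infer that the plan hides sedation that Shoden is known to cause. The documents do not support that. O.1 ties the reported somnolence and drowsiness to other Withania products and describes Shoden's own trials as free of significant adverse events. The sleep findings in E.1 make drowsiness plausible, but they are not adverse-event reports. A reader might also infer a bias that always favours good tolerability. The restriction continues past dosing, so the error can run in either direction.

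**Conclusion.** The gap is real and modest. No adverse-event baseline is both unexposed and free of the caffeine restriction, and N.1 is categorical about symptoms already present, so mild drowsiness or fatigue can be misclassified. The effect is limited for single-dose events. It is largest in the four-week phase if the 48-hour questionnaire is dropped, where a restricted baseline against unrestricted follow-up tends towards under-attribution.

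The size is unknown. The documents give neither the share of regular caffeine users nor a rate of withdrawal symptoms, so no count of affected participants can be supported. The percentages above rest on assumed p and w, on independence, and on masking alone.

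Both periods carry the same restriction, so the dose comparison suffers less than the absolute rates. The Aim 2 statement on severe events and the stopping rule on serious events are unlikely to turn on mild drowsiness. This is a cheap improvement to the attribution data, not a fault that undermines the trial.

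**What to change.** 1. Add the existing adverse-event questionnaire at screening. Baseline Visit 1 is at least three days later, so screening falls at least 72 − 48 = 24 hours before the caffeine restriction starts.
2. Repeat it shortly before the restriction begins in period 2, for example with the pre-visit call or the REDCap contact, timed more than 48 hours before the visit.
3. Record usual caffeine intake at screening.
4. In N.1, keep the start-of-visit questionnaire as the reference for single-dose events. Name the pre-restriction questionnaire as the reference for the four-week phase, including when the 48-hour visit is eliminated, and align I.4.2 with this.
5. Flag symptoms first seen at the start of a baseline visit as diet- or fasting-period symptoms.

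The cost is two short questionnaires and one question per participant at contacts already planned, two entries in Table 1, and a few sentences in N.1 and I.4.2. Nothing in the diet or the dosing needs to change.

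### Read literally, inclusion criterion 8 and the baseline halt rule overlap: a participant with one of hemoglobin and hematocrit above its limit and the other below is both eligible and withdrawn

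*Combined protocol and SAP*

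**What the plan says.** **Entry (F.2.2, inclusion criterion 8).** For men the test is "Hemoglobin ≥ 13.0 g/dL or hematocrit" of at least 39%. For women it is "hemoglobin ≥ 12.5 g/dL or hematocrit" of at least 38%. Both are given "per FDA recommendations on blood donation". One passing value is enough.

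**Halt (I.4.1, Tolerability and safety).** "If the baseline CBC shows hemoglobin or hematocrit levels below what is recommended by the FDA for blood donation, the visit will be halted" at once. No limits are restated; the rule refers only to the FDA recommendation.

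**What follows a halt (same paragraph).** "Participants will be asked to stay for 2.5 hours after the study agent has been administered to assess for acute side effects". The end-of-visit adverse events questionnaire moves to the phone, and the missed 7-hour, 10-hour and 12-hour safety checks move to the 24-hour visit. Then: "After the 24-hour visit, the participant will be withdrawn from the study". By contrast, the next paragraph lets a participant stay in the study when trouble with blood sampling was the only reason for stopping the visit.

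**Order of events.** I.4.1 places the blood count among the safety labs of the baseline visit. H.1 has the product taken after baseline measurements. Neither section says that the blood count result must be known before the capsules are given.

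**Room for losses.** F.2.1 plans 12 enrolled, two dropouts and 10 completers. L.4 bases its power on those 10.

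**The concern.** The entry test is worded as a pass and the halt test as a fail, and both join the two measurements with 'or'. Such rules are not opposites. The first needs one good value and the second needs one bad value, so a person with one of each satisfies both. Screening would admit that person, and the baseline visit would remove the same person although nothing in the blood had changed.

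The halt paragraph also reads as written for someone who has already taken the product. A discordant participant could therefore be dosed and then withdrawn on values that the entry criterion accepts.

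The statistical stake is the pairing. L.1 compares the two doses within person by paired tests on Cmax, AUC and half-life. A participant withdrawn at either baseline visit does not supply a complete pair. With 12 enrolled and two dropouts allowed for, each avoidable loss counts.

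**Working it through.** **1. The two rules side by side.** Let H mean that hemoglobin is at or above its limit, and C that hematocrit is.

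- Entry: H or C.
- Halt, read literally: not-H or not-C, which is the same as not (H and C).
- The two overlap whenever exactly one of H and C is true.

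The values below are chosen only to show the logic. Limits are 13.0 g/dL and 39% for men, 12.5 g/dL and 38% for women.

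| Sex | Hemoglobin (g/dL) | Hematocrit (%) | Meets criterion 8 | Halted (literal) | Conflict |
|---|---|---|---|---|---|
| M | 12.8 | 38.5 | no | yes | no |
| M | 12.8 | 39.5 | yes | yes | **yes** |
| M | 13.2 | 38.5 | yes | yes | **yes** |
| M | 13.2 | 39.5 | yes | no | no |
| F | 12.3 | 37.5 | no | yes | no |
| F | 12.3 | 38.5 | yes | yes | **yes** |
| F | 12.7 | 37.5 | yes | yes | **yes** |
| F | 12.7 | 38.5 | yes | no | no |

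Two of the four pass/fail combinations in each sex both qualify and halt. That counts logical cases; it says nothing about how often they occur.

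**2. When the conflict disappears.** The halt must be the exact complement of entry. The complement of (H or C) is (not-H and not-C); the complement of (H and C) is (not-H or not-C). Either pairing leaves no combination that both qualifies and halts. In each, the pass-worded rule and the fail-worded rule carry opposite connectors. Using the same connector in both, as the text now does, leaves the overlap in place.

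**3. Timing.** A 2.5-hour stay counted from administration, and 7-hour and 10-hour evaluations counted as missed, have meaning only after a dose. With no step that holds the dose for the result, the text allows dosing first.

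**4. What a lost pair costs.** Inputs from L.4 and L.1: paired t-test, two-sided alpha 0.05, d = 1.3, n = 10, stated power 95%. Power is the probability that a noncentral t variable with n − 1 degrees of freedom and noncentrality d√n falls beyond the two-sided critical value.

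- n = 10: noncentrality 1.3 × √10 = 4.11, power 95.4%. This reproduces the plan's 95%.
- n = 9: 1.3 × 3 = 3.90, power 92.5%.
- n = 8: 1.3 × √8 = 3.68, power 88.2%.
- n = 7: 1.3 × √7 = 3.44, power 81.6%.

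These are losses beyond the two already planned. A halted participant who counts as one of those two leaves the stated power unchanged.

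**The case against.** The strongest reply is that the halt rule sets no separate limit for each measurement. It refers to the FDA recommendation, which criterion 8 presents as an either/or test. Falling below that recommendation could then mean failing the whole test, and nothing would conflict. This reading is possible, and it means that the two rules cannot be called contradictory beyond doubt. But I.4.1 does not state it, and its plain wording points the other way. A rule that ends participation should not depend on which reading staff adopt on the day.

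Second, I.3 has the study clinician review screening results and excludes anyone with an abnormal laboratory evaluation. This may remove some borderline people. However, abnormal is not defined or tied to these limits, and excluding someone who meets criterion 8 on these same values would itself sit badly with that criterion.

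Third, the order of result and dose is inferred, not stated, and the 2.5-hour sentence recurs in the paragraph on sampling difficulties. That is correct. The inference is still strong, because the halt paragraph has no branch for a participant who has not been dosed.

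Fourth, the power loss is modest: three losses beyond the planned two still leave 81.6% at the planned effect size. This stands, and it limits the statistical weight of the point.

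**Conclusion.** The point holds as a literal overlap that needs reconciling, confined to participants with one value above and one below its limit. For them, values that satisfy entry also end participation, probably after a dose. How many of the 12 would be affected cannot be derived from the documents and may be none. Each one is an exposure without a complete dose pair.

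A reader might infer more, but the documents do not support it:

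- **That study blood draws before Baseline Visit 2 make this conflict more frequent.** The rule does apply again there, and I.4.1 puts one baseline visit at 175 mL. But no effect on hemoglobin is given, and a person with both values below the limits would be halted under either reconciled rule. That is not a product of the mismatch.
- **That the losses bias the PK results.** No link between low-normal blood counts and withanolide exposure is documented.
- **That women are mainly affected, because their limits have a ratio of 38/12.5 = 3.04 against 39/13.0 = 3.00 for men.** This needs a fixed hematocrit-to-hemoglobin ratio, which the documents do not supply.
- **That the primary comparison needs a full 48-hour profile from everyone.** I.4.2 allows the 48-hour point to be dropped after the first two participants.

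**What to change.** Reconcile criterion 8 in F.2.2 with the halt paragraph in I.4.1 so that no set of values meeting entry also triggers the halt. The halt condition should be the exact logical complement of the entry condition. Asking only for the same connector in both places would not work, since both already use 'or'. The halt paragraph should cite criterion 8 or restate its limits, so that only one reading is possible. Which rule to adopt is the sponsor's decision.

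Also reconcile the halt paragraph with the dosing sequence in I.4.1 by stating whether the blood count result is to be available before dosing.

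The cost is a short wording amendment. Making the two rules consistent adds no visit or sample. There may be a few more screen failures if the reconciled entry test is the narrower one; F.2.1 expects to screen about 20 to enrol 12. If the sponsor decides that the result must come first, laboratory turnaround could affect when the 13-hour visit starts; the documents give no turnaround time.
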